5.3 Re-Screening of Patients

Patients may not be enrolled more than once.

5.4 Removal of Patients from Therapy or Assessment

Aerogen Pharma or the Investigator may discontinue patients from the study at any time for safety or administrative reasons.

All patients who discontinue from the study are to complete the End of Study procedures (except Screen Failure patients).

The Investigator will promptly explain to the patient involved that the study will be discontinued for the patient and provide appropriate medical treatment and other necessary measures for the patient.

Patients who discontinue early from the study will be discontinued for one of these primary reasons: Adverse events, patient death, lost to follow-up, patient withdrew consent, protocol violation, lack of efficacy, investigator decision, study terminated by sponsor, screen failure, or other. Study disposition information will be collected on the Patient Disposition CRF.

5.4.1 Criteria for Patient Conversion to Conventional Therapy

At any time during VentaProst administration, patients will be crossed-over to standard of care therapy with aerosolized Veletri if they meet one or more of the following pre-defined criteria for a deterioration in their condition:

- Severe postoperative mediastinal bleeding (> 500 mL/hr)

- Hemoptysis
- If a clinically inadequate response to VentaProst is observed, the patient may be converted back to aerosolized Veletri administered in accordance with each site's standard of care guidelines at the investigator's discretion

Additionally, patients will be crossed-over to standard of care therapy with aerosolized Veletri after extubation.

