Criteria for Conversion to Conventional Therapy	
At any time during VentaProst administration, patients will be crossed over to standard therapy of aerosolized Veletri if they meet one or more of the following pre-defined criteria for a deterioration in their condition:
 
 • Severe postoperative mediastinal bleeding (> 500 mL/hr) • Hemoptysis • If a clinically inadequate response to VentaProst is observed, the patient may be converted back to aerosolized Veletri administered in accordance with each site's standard of care guidelines at the investigator's discretion 
Additionally, patients will be crossed over to standard of care therapy with aerosolized Veletri after extubation.

Statistical Methods	
All patients who are enrolled in the study and who receive at least one dose of VentaProst will be included in the intent-to-treat (ITT) analyses of pharmacodynamic and safety data. All available data will be used and missing data will not be estimated or carried forward in any statistical summary or analyses.
 
Descriptive summary statistics include the number of patients, mean, median, percent coefficient of variation (%CV) (if required), standard deviation, and minimum and maximum values (quantitative variables) or the number of patients and percentages by category (qualitative variables). Changes will be assessed as the difference between baseline measurements and the appropriate post-dose measurements unless otherwise specified. Individual patient listings of data will also be provided to allow for review of all

	
pharmacodynamic, safety, and tolerability parameters.
 
The number of patients has been selected to enable an adequate clinical assessment of pharmacodynamic, safety, and tolerability parameters without presenting undue risk to a large number of patient's exposure to this investigational product.
 
Further details will be included in the Statistical Analysis Plan.

Efficacy Analysis	Efficacy will be secondarily determined by summarizing success or failure to meet the pharmacodynamics goals of the study.
Safety Analyses	Safety data will be summarized using frequencies and incidence rates.

Table 1 – Schedule of Assessments and Procedures – Part I

Study Procedures	Screening	Intra-Operative	Aerosolized Veletri Treatment Period (OR/ICU)	VentaProst Treatment Period (ICU)	End of Study
Written Informed Consent	X				
Demographics	X				
Assign Patient ID	X				
Medical History	X				

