2. BACKGROUND AND RATIONALE

2.1 Introduction

Aerogen Pharma is developing VentaProst, an inhaled epoprostenol, as an integrated medication/device combination product consisting of a FDA-approved and commercially available epoprostenol sodium intravenous (IV) solution (Flolan®) administered by a precision single-patient use custom nebulizer compatible with ventilator support equipment used in operating rooms (ORs) and intensive care units (ICUs). VentaProst is being investigated as a perioperative pulmonary vasodilator for patients undergoing cardiac surgery with cardiopulmonary bypass (CPB). VentaProst therapy will be transferable from anesthesia ventilator to patient transport to ICU ventilator and on to nasal cannula post-extubation, thus maintaining vasodilation and preventing rebound pulmonary hypertension (PH) during patient transition from surgery.

Flolan (epoprostenol sodium), also known as prostacyclin, PGI₂ or PGX, a metabolite of arachidonic acid, is a naturally occurring prostaglandin. Epoprostenol has two major pharmacological actions: (1) direct vasodilation of pulmonary and systemic arterial vascular beds, and (2) inhibition of platelet aggregation. In animals, the vasodilatory effects of epoprostenol reduce right and left ventricular afterload and increase cardiac output (CO) and stroke volume.

Epoprostenol is rapidly hydrolyzed at neutral blood pH and is also subject to enzymatic degradation. No available chemical assay is sufficiently sensitive and specific to assess the *in vivo* human pharmacokinetics (PK) of epoprostenol. Animal studies using tritium-labelled epoprostenol have indicated a high clearance (93 mL/min/kg), small volume of distribution (357 mL/kg), and a short half-life (2.7 minutes). During infusions in animals, steady-state plasma concentrations of tritium-labelled epoprostenol were reached within 15 minutes and were proportional to infusion rates.

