2.2.5 Summary of Known and Potential Risks of Inhaled Epoprostenol Administration

Safety of inhaled epoprostenol in cardiothoracic surgery patients is remarkable. In the reported literature to date, there were no reports of serious or life-threatening drug-related safety events. Due to its mechanism of action, inhaled epoprostenol may theoretically cause increased bleeding (anti-platelet mechanism) or systemic vasodilation consequent to spill over into the central circulatory system, but no such events have been reported. Some accounts of the use of inhaled prostacyclin in the chronic setting (e.g. iloprost for PAH) report transient events as listed on the approved product labeling. These include cough, headache, flushing, and an influenza-like syndrome. However, these types of events are unlikely to be reported due to sedation in the ICU setting.

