4.5 Intra-Operative/ICU

In Part I, approximately 10 cardiac surgery patients on CPB who meet entry criteria will be entered into the study and will receive conventionally-administered aerosolized Veletri (in accordance with each site's standard of care guidelines) in the OR or ICU. Once clinically defined hemodynamic effects are achieved in the ICU, the aerosolized epoprostenol will be stopped and patients will be crossed-over to a calculated VentaProst equivalent dose of 17 ng/kg/min. The VentaProst dose will then be increased in 20% increments (refer to VentaProst Pharmacy Manual) every 15 minutes to match the PD measures achieved with the aerosolized Veletri dose.

In Part II, approximately 10 cardiac surgery patients on CPB who meet study entry criteria will be entered into the study and will be assigned to receive a starting dose of 3.4 ng/kg/min of VentaProst in the OR or ICU. The VentaProst dose will then be increased in 3.4 ng/kg/min increments (refer to VentaProst Pharmacy Manual) every 5 to 15 minutes as clinically indicated until no further improvements in one or more hemodynamic parameters are achieved.

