6. STUDY TREATMENTS

6.1 Identity of Medication Component of the Investigational Product

The study medication of VentaProst, Flolan (epoprostenol sodium), is manufactured by GlaxoSmithKline and has been analyzed and released according to their specifications. The clinical label will identify the product by name, lot number, Sponsor, storage conditions, and indicate that it is limited to investigational use only.

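### For severe bleeding or hemoptysis on VentaProst, section 5.4.1 directs a switch to aerosolized Veletri, so epoprostenol continues by default and stopping it is not named as an option

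*Combined protocol and SAP*

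**What the plan says.** Section 5.4.1 states, for anyone receiving VentaProst, that "patients will be crossed-over to standard of care therapy with aerosolized Veletri if they meet one or more of the following pre-defined criteria". Three criteria follow.

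- The first is "Severe postoperative mediastinal bleeding (> 500 mL/hr").
- The second is hemoptysis, with no threshold.
- The third is worded differently: "If a clinically inadequate response to VentaProst is observed, the patient may be converted back to aerosolized Veletri", and this is left to the investigator's discretion.

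A separate sentence moves patients to Veletri after extubation. The synopsis carries the same rule: "patients will be crossed over to standard therapy of aerosolized Veletri if they meet one or more of the following".

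On the drug itself, section 6.1 identifies "The study medication of VentaProst, Flolan (epoprostenol sodium"). Section 4.5 treats Veletri as the same substance when it describes the Part I switch: "the aerosolized epoprostenol will be stopped and patients will be crossed-over to a calculated VentaProst equivalent dose". Section 2.1 says: "Epoprostenol has two major pharmacological actions: (1) direct vasodilation of pulmonary and systemic arterial vascular beds, and (2) inhibition of platelet aggregation". Section 2.2.5 adds that "inhaled epoprostenol may theoretically cause increased bleeding (anti-platelet mechanism"), and then says that no such events have been reported.

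**The concern.** When a patient bleeds heavily on a drug that inhibits platelets, a clinician will ask whether to stop the drug. The specific rule does not raise that question. It answers a different one, namely which device should deliver epoprostenol. The risk in section 2.2.5 is attached to the drug and not to the nebulizer, so changing the device does not address it.

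The wording also separates the criteria. Discretion is stated for inadequate response and is absent for the two bleeding events, so an investigator who reads the section closely will take the switch as required for those two. In Part II the effect can be odder still. Sections 4.2 and 5.1 do not require prior Veletri for those patients, so following the rule may mean starting a second epoprostenol product during a hemorrhage.

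What is at stake is the safety instruction that a bedside team would reach for first in an acute bleed.

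**Working it through.** The plan states no figure on this point, so the check is textual.

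1. **Is the switch required for bleeding?** The opening sentence in both section 5.4.1 and the synopsis uses *will*. Of the three criteria, two (mediastinal bleeding and hemoptysis) have no softening words, and one (inadequate response) has *may* and names investigator discretion. On its face, the switch is directed for the two bleeding criteria.

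2. **Does the switch keep the patient on the same drug?** Section 6.1 gives epoprostenol sodium as the VentaProst medication. Section 4.5 calls the Veletri given before cross-over aerosolized epoprostenol. Both sides of the switch are inhaled epoprostenol.

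3. **Does the protocol link that drug to bleeding?** Yes, in theory. Section 2.1 lists platelet inhibition as one of two major actions, and section 2.2.5 derives a theoretical bleeding risk from it. Section 2.2.5 also limits the link, because it knows of no reported events.

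4. **Does any other section tell sites to stop, reduce or withhold epoprostenol for bleeding?** None does. The weaning instructions in sections 4.1, 6.3.5 and 10 respond to hemodynamic instability and falling oxygenation, and do not mention bleeding.

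5. **What authority is there to stop it?** Section 5.4, the parent section, lets the investigator discontinue a patient for safety and requires appropriate medical treatment. Section 13.2.1 preserves immediate action for safety. Against these, section 13.2.1 also says that protocols are followed as written, and section 13.2.2 asks for strict adherence. The general authority exists, but it has to be set against a specific instruction pointing the other way.

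6. **How often would the rule apply?** About 10 patients are planned per part, so about 10 + 10 = 20 in all. The documents give no rate for either bleeding event and no relation between epoprostenol exposure and bleeding. Neither the number of patients affected nor the harm to them can be derived.

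**The case against.** There is a good case for the rule. It takes a deteriorating patient off a product that, by section 2.2.2, has never been in a clinical trial, and returns that patient to standard of care. Under section 5.1 these patients clinically require the treatment, and the weaning sections warn of rebound. Section 2.1 says that inhalation keeps systemic exposure low, and section 5.2 excludes bleeding disorders, anticoagulated thromboembolic disease and low platelet counts. Section 5.4.1 fixes no Veletri dose or duration, so after the handover site guidelines govern, and these may contain bleeding rules that we cannot see. The section's *will* is also not strict throughout, since the discretionary third item sits under the same opening sentence.

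Most of this stands, and it limits the severity. The exit from the investigational product is sound and should stay. What the objection does not remove is the direction of the default: for the two bleeding criteria the stated destination is more epoprostenol, and nothing in that rule says that stopping is open.

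A reader might infer two stronger things.

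- **That the investigator is compelled to continue epoprostenol.** The documents do not support this. Sections 5.4 and 13.2.1 allow it to be stopped, and section 5.4.1 does not forbid stopping.
- **That conversion raises the dose, notably in Part II.** Taking the planned equivalence of 50 ng/kg/min Veletri to 17 ng/kg/min VentaProst, a patient at the 3.4 ng/kg/min starting dose receives the equivalent of 3.4 × 50/17 = 10 ng/kg/min Veletri. Conversion to the nominal 50 would then be 50/10 = 5 times as much. But section 5.4.1 does not prescribe 50, and a site that matched doses would give a ratio of 1. The equivalence is itself an estimate that the trial is meant to test. No dose increase can be claimed.

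**Conclusion.** The point holds as a minor one. The specific rule for severe mediastinal bleeding and hemoptysis has a poor default: it continues, by another device, the drug whose anti-platelet action the protocol names as a theoretical bleeding risk. Withholding that drug is left to general safety clauses.

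The size is a low-cost safety correction and no more. The risk is theoretical, with no events reported according to section 2.2.5, and no harm can be quantified from the documents. The conclusion rests on reading *will* in section 5.4.1 and the synopsis as directive for the two bleeding criteria, which the contrast with the third criterion supports. It also rests on the absence of any bleeding-specific instruction elsewhere in the protocol. Site guidelines were not available and might already cover the matter in practice.

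**What to change.** Amend section 5.4.1 and the matching synopsis entry. For mediastinal bleeding above 500 mL/hr or hemoptysis, state that VentaProst is discontinued. State also that the investigator decides whether to stop inhaled epoprostenol or to continue it as aerosolized Veletri, and at what dose, weighing bleeding against rebound. The decision is noted in the medical record. That note is needed because section 6.6 captures therapies that were given and would not show a decision to withhold one.

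Leave the inadequate-response rule and the post-extubation rule as they are. Do not add an option to step VentaProst down gradually in these patients, since that would keep a bleeding patient on the investigational product, which the current rule removes.

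The cost is one small safety amendment, needing IRB approval at about three sites under section 13.2.1, with no extra patients, visits or procedures. The clinical downside is possible rebound when epoprostenol is stopped in a patient who needs it, which is why continuation on Veletri remains open.

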6. STUDY TREATMENTS

6.1 Identity of Medication Component of the Investigational Product

The study medication of VentaProst, Flolan (epoprostenol sodium), is manufactured by GlaxoSmithKline and has been analyzed and released according to their specifications. The clinical label will identify the product by name, lot number, Sponsor, storage conditions, and indicate that it is limited to investigational use only.

6.1.1 Storage Condition

Both the vials of study medication and sterile diluent buffer should be stored between 20° to 25°C (68° to 77°F) with excursions permitted to 15° to 30°C (59° to 86°F) and kept in the supplied carton to protect the product from light. Study medication will be stored in a secure, controlled-access location at the study sites.

6.2 Treatments Administered

6.2.1 Part I

Post-cardiac surgical patients will initially receive treatment with aerosolized Veletri 50 ng/kg/min in either the OR or the ICU in accordance with each site's standard of care guidelines on administration of aerosolized Veletri. In the ICU, patients who demonstrate at least a 15% improvement in one or more hemodynamic parameters with aerosolized Veletri will be crossed over to a calculated VentaProst equivalent dose of 17 ng/kg/min. The VentaProst dose will then be increased in 20% increments (refer to VentaProst Pharmacy Manual) every 15 minutes to match the clinically meaningful PD measures achieved (i.e., not less than 90% of the effect observed) with the aerosolized Veletri dose.

6.2.2 Part II

In the OR or the ICU, post-cardiac surgical patients will receive VentaProst at a starting dose of 3.4 ng/kg/min of VentaProst, followed by dose titration up in 3.4 ng/kg/min increments (refer to VentaProst Pharmacy Manual) every 5 to 15 minutes as clinically indicated until clinically meaningful hemodynamic effects are achieved (i.e., at least a 15% improvement in one or more hemodynamic parameters).

6.3 Study Medication Supply, Preparation, and Administration

6.3.1 Study Medication Supply

The medicinal component of VentaProst, Flolan, will be supplied as a lyophilized

formulation of 1.5 mg of epoprostenol sodium in single-use 17 mL glass vials with gray butyl rubber closures, along with the required sterile diluent buffer for reconstitution in glass vials containing 50 mL of 94 mg glycine, 73.3 mg sodium chloride, sodium hydroxide (added to adjust pH), and Water for Injection, USP.

The patient number and dose number will be recorded on the study medication carton and vial. The patient number, dose number, date and time of dose administration will be recorded in the study medication dispensing logs.

6.3.2 Study Medication Preparation

Refer to the VentaProst Pharmacy Manual for preparation of the study medication for aerosol administration.

Prior to use, reconstituted solutions of epoprostenol sodium must be protected from light and must be refrigerated at 2° to 8°C (36° to 46°F) if not used immediately. Do not freeze reconstituted solutions of epoprostenol sodium for injection and discard any reconstituted solution that has been frozen. Discard any reconstituted solution if it has been refrigerated for more than 48 hours.

During use, a single reservoir of reconstituted solution of epoprostenol sodium can be administered at room temperature for a total duration of eight hours and protect the reconstituted product from temperatures greater than 25°C (77°F) and less than 0°C (32°F) and do not expose to direct sunlight.

6.3.3 Study Medication Administration

6.3.3.1 Part I

Aerosolized Veletri 50 ng/kg/min will be administered to study patients in the OR or the ICU in accordance with each site's standard of care guidelines on administration of aerosolized Veletri. In the ICU, patients who demonstrate a clinically meaningful hemodynamic response (i.e., at least a 15% improvement in one or more hemodynamic parameters) to aerosolized Veletri will be crossed over to a calculated VentaProst equivalent dose of 17 ng/kg/min to be administered through a custom nebulizer delivery system. The VentaProst dose will then be increased in 20% increments (refer to VentaProst Pharmacy Manual) every 15 minutes to match the clinically meaningful PD measures achieved (i.e., not less than 90% of the effect observed) with the aerosolized Veletri dose.

6.3.3.2 Part II

In the OR or ICU, patients will receive a starting dose of 3.4 ng/kg/min of VentaProst. The VentaProst dose will be titrated up or down in 3.4 ng/kg/min increments (refer to VentaProst Pharmacy Manual) every 5 to 15 minutes as clinically indicated until clinically meaningful hemodynamic effects are achieved (i.e., at least a 15% improvement in one or more hemodynamic parameters).

6.3.4 Study Medication Titration

6.3.4.1 Part I

In the ICU, the VentaProst dose will be increased in 20% increments (refer to VentaProst Pharmacy Manual) every 15 minutes to match the clinically meaningful hemodynamic effects achieved with the conventionally administered aerosolized Veletri. Once clinically meaningful hemodynamic effects are achieved (i.e., not less than 90% of the effect observed), the VentaProst dose will be maintained for at least 15 minutes.

6.3.4.2 Part II

In the OR or ICU, the patient will have their VentaProst dose titrated up in 3.4 ng/kg/min increments (refer to VentaProst Pharmacy Manual) every 5 to 15 minutes as clinically indicated until clinically meaningful PD endpoints are achieved (i.e., at least a 15% improvement in one or more hemodynamic parameters) and the dose stabilized. If the patient fails to achieve clinically meaningful PD endpoints, VentaProst dose escalation will continue until dose-limiting pharmacological effects are elicited or a tolerance limit to VentaProst is established.

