4.2 Part II

The second part of the study will be conducted in approximately 10 consented cardiothoracic surgical patients on CPB with perioperative pulmonary hypertension (mPAP > 25 mm Hg). This part of the study is designed to establish a dose response relationship of VentaProst to PD effect by dose escalation in these patients. The goal will be to determine the VentaProst dose necessary to achieve at least a 15% improvement in one or more hemodynamic parameters (as defined by the clinical team).

Hemodynamic measurements will be taken prior cardiac surgery (after induction) with CPB, prior to dosing with VentaProst, and after each dose titration step.

Qualifying patients will:

- Receive a starting dose of 3.4 ng/kg/min of VentaProst
- Have hemodynamic parameters monitored and recorded
- Receive increase in the VentaProst dose in 3.4 ng/kg/min increments (refer to VentaProst Pharmacy Manual)
 - *IF A GREATER THAN A 15% IMPROVEMENT IN ONE OR MORE HEMODYNAMIC PARAMETERS (AS DEFINED BY THE CLINICAL TEAM) IS SEEN WITH THE INITIAL VENTAPROST DOSE, but NO additional clinically meaningful change is seen with this first dose escalation:*
 - Have the VentaProst dose reduced to the initial dose level
 - *IF A GREATER THAN A 15% IMPROVEMENT IN ONE OR MORE HEMODYNAMIC PARAMETERS (AS DEFINED BY THE CLINICAL TEAM) IS SEEN WITH THE INITIAL VENTAPROST DOSE, but AN additional clinically meaningful change is seen with the first dose escalation:*
 - Continue to receive VentaProst in increasing steps of 3.4 ng/kg/min every 5 to 15 minutes as clinically indicated until no further improvements in one or more hemodynamic parameters are achieved or until dose-limiting pharmacological effects are elicited or a tolerance limit to VentaProst is established.

- *IF A LESS THAN A 15% IMPROVEMENT IN ONE OR MORE HEMODYNAMIC PARAMETERS (AS DEFINED BY THE CLINICAL TEAM) IS SEEN WITH FIRST DOSE INCREASE:*
 - Continue to receive VentaProst in increasing steps of 3.4 ng/kg/min every 5 to 15 minutes as clinically indicated until no further improvements in one or more hemodynamic parameters are achieved or until dose-limiting pharmacological effects are elicited or a tolerance limit to VentaProst is established.

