 - Reduce the VentaProst dose to the previous dose level (after the VentaProst dose has stabilized) at which the one or more hemodynamic parameters showed maximum improvement. The VentaProst dose level will remain at this setting until clinical conditions determine the need for changing the dose.

Arterial and central venous blood oxygenation parameters will also be considered in the titration process.

Hemodynamic, oxygenation, and ventilator parameters will be obtained at the time of each VentaProst dose adjustment in the ICU.

Patients requiring post-operative support with epoprostenol will be allowed to continue on VentaProst treatment in the ICU as long as they are still on mechanical ventilation. For weaning, doses will be decreased in increments of 20% of the VentaProst equivalent dose, with a minimum of 30 minutes between changes, down to 20% of the dose before discontinuation (see Section 4.1, Weaning Guideline in Part I above). If the patient is extubated and placed on institution's standard of care delivery system for administering aerosolized Veletri, weaning from aerosolized Veletri will follow each institution's guideline.

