10.2.3 VentaProst Treatment (OR/ICU)

10.2.3.1 Dosing

The patient will undergo the following study-related procedures and evaluations:

- Patients will receive a starting dose of 3.4 ng/kg/min of VentaProst
- Patients will receive increases in VentaProst dose by 3.4 ng/kg/min (refer to VentaProst Pharmacy Manual)
 - If greater than a 15% improvement in one or more hemodynamic parameters (as defined by the clinical team) is seen with the initial VentaProst dose, but NO additional clinically meaningful change is seen with the first dose escalation, the VentaProst dose will be reduced to the initial dose level
 - If greater than a 15% improvement in one or more hemodynamic parameters (as defined by the clinical team) is seen with the initial VentaProst dose, but AN additional clinically meaningful change is seen with the first dose escalation, continue to dose with VentaProst in increasing steps of 3.4 ng/kg/min every 5 to 15 minutes as clinically indicated until no further improvements in one or more hemodynamic

parameters are achieved or until dose-limiting pharmacological effects are elicited or a tolerance limit to VentaProst is established

- If less than a 15% improvement in one or more hemodynamic parameters (as defined by the clinical team) is seen with first dose increase, continue to dose with VentaProst in increasing steps of 3.4 ng/kg/min every 5 to 15 minutes as clinically indicated until no further improvements in one or more hemodynamic parameters are achieved or until dose-limiting pharmacological effects are elicited or a tolerance limit to VentaProst is established. After the VentaProst has been stabilized, reduce the VentaProst dose to the previous dose level at which a hemodynamic parameter showed maximum improvement. The VentaProst dose level will remain at this setting until clinical conditions determine the need for changing the dose
- Measure hemodynamic, oxygenation, and ventilator parameters at each dose adjustment
- Record all concomitant medications
- Record AEs

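### Part II gives two incompatible rules for when upward titration stops: at a 15% improvement (Section 6) or at a response plateau (synopsis, 4.2, 10.2.3.1)

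*Combined protocol and SAP*

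**What the plan says.** All places are in the protocol.

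**Threshold rule (Section 6).** Section 6.3.4.2 titrates upward "until clinically meaningful PD endpoints are achieved (i.e., at least a 15% improvement in one or more hemodynamic parameters) and the dose stabilized". Its next sentence deals with patients who do not get there: "If the patient fails to achieve clinically meaningful PD endpoints, VentaProst dose escalation will continue until dose-limiting pharmacological effects are elicited", or until a tolerance limit is found. It mentions neither a plateau nor a return to a lower dose. Section 6.3.3.2 says "The VentaProst dose will be titrated up or down in 3.4 ng/kg/min increments" and sets the same target: "until clinically meaningful hemodynamic effects are achieved (i.e., at least a 15% improvement in one or more hemodynamic parameters". Section 6.2.2 matches it, but for upward titration only.

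**Plateau rule (synopsis, 4.2, 10.2.3.1).** In 4.2, a patient already above 15% at the starting dose still receives a first escalation. If that brings more benefit, steps continue "until no further improvements in one or more hemodynamic parameters are achieved or until dose-limiting pharmacological effects are elicited or a tolerance limit" is reached. The same stop applies to a patient below 15% at the first increase. Section 4.2 then adds, as a separate item, "Reduce the VentaProst dose to the previous dose level (after the VentaProst dose has stabilized"), meaning the level with the greatest improvement. The synopsis matches this, and its treatment paragraph states the step-back at plateau in general terms.

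Section 10.2.3.1 has the same branches ("continue to dose with VentaProst in increasing steps of 3.4 ng/kg/min every 5 to 15 minutes as clinically indicated until no further improvements"), but its step-backs are narrower. If the first escalation adds nothing, "the VentaProst dose will be reduced to the initial dose level". The return to the level of greatest improvement is written only inside the under-15% branch. Section 4.5 gives the plateau stop and no step-back.

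**Purpose.** Section 4.2 says that Part II is meant to establish a dose response by escalation. It then gives the goal as finding the dose that achieves at least a 15% improvement.

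**The concern.** Two sets of sections govern the same act on the same patient and end it at different points. The difference goes in opposite directions for responders and non-responders.

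- **Responders.** Section 6 ends escalation at the 15% dose, so nothing is observed above it in the upward phase. The part of the study meant to show a dose response would not see the upper part of the curve in these patients.
- **Patients who plateau below 15%.** Section 6.3.4.2 pushes them beyond the point at which 4.2 and 10.2.3.1 would stop and step back. Section 2.2.2 reports no previous clinical trials of VentaProst, so escalation past a plateau should not happen by drafting accident.

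With about 10 patients at about three sites, a few handled under the other rule would put threshold doses and plateau doses into one summary. The dose on which a patient is maintained, and from which weaning starts, would differ as well.

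**Working it through.** The protocol gives no figure to reproduce here. The check sets the two rules side by side and follows the dose.

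**Inputs.** The starting dose and the step are both 3.4 ng/kg/min (4.2, 10.2.3.1), so the dose at level j is 3.4 × j. Every bound below assumes that no dose-limiting effect or tolerance limit stops escalation first.

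**Formulas.**
- Responder who first reaches 15% at level k: Section 6 tops out at 3.4 × k. The plateau rule needs at least one more level to see that nothing further is gained, so at least 3.4 × (k + 1).
- Patient whose best response is below 15% and occurs at level m: the plateau rule goes to 3.4 × (m + 1) and returns to 3.4 × m. Section 6.3.4.2 has no plateau stop, so it goes to at least 3.4 × (m + 2).

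| Patient | Section 6 | Plateau rule |
|---|---|---|
| Above 15% at the starting dose (k = 1) | 3.4 × 1 = 3.4 | at least 3.4 × 2 = 6.8 before any step-back |
| First reaches 15% at level 3 (k = 3) | 3.4 × 3 = 10.2 | at least 3.4 × 4 = 13.6 before any step-back |
| Best response below 15%, at level 2 (m = 2) | at least 3.4 × 4 = 13.6, no return stated | 3.4 × 3 = 10.2, then back to 3.4 × 2 = 6.8 |

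**Gap at k = 2.** The branches in 4.2 and 10.2.3.1 cover more than 15% at the initial dose, and less than 15% at the first increase. A patient below 15% at 3.4 who reaches 15% at 6.8 fits neither. A patient with exactly 15% at 3.4 is not covered by the initial-dose branches, which require more than 15%. For these patients only the general statements in the synopsis treatment paragraph and 4.5 supply a plateau rule.

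**Illustration with assumed responses.** Suppose improvements of 16%, 24%, 30% and 30% at 3.4, 6.8, 10.2 and 13.6 ng/kg/min. Section 6 stops at 3.4. The synopsis and 4.2 go to 13.6 and return to 10.2, and 10.2 / 3.4 = 3 times the Section 6 dose. Read literally, 10.2.3.1 (for this branch) and 4.5 state no return from 13.6. If the responses were 16% and 16%, the final dose would be 3.4 under both Section 6 and 4.2, but 4.2 would have tested 6.8 on the way.

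**Lower doses seen in weaning.** Section 10.2.3.2 weans in steps of 20% of the dose, with readings around each change. From 3.4 this gives 0.8 × 3.4 = 2.72, 0.6 × 3.4 = 2.04, 0.4 × 3.4 = 1.36 and 0.2 × 3.4 = 0.68 ng/kg/min, if the patient is still ventilated.

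**The case against.** **Wording that might reconcile the rules.** Both sets of sections leave the steps to clinical indication, 6.3.4.2 adds that the dose be stabilized, and 6.3.3.2 allows movement down as well as up.
- Clinical discretion softens the lower bounds, but it appears under both rules and does not choose between them.
- The stabilization wording is absent from 6.2.2 and 6.3.3.2, and the next sentence of 6.3.4.2 ties further escalation to failure to reach 15%.
- Downward movement fits a step-back, but 6.3.3.2 still names 15% as the target.
- Section 10 calls itself the detailed description, but nothing gives it precedence over Section 6.

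**Section 6 serves the stated goal.** This stands in part. The goal sentence in 4.2 and the synopsis is the 15% dose, so the tension between threshold and plateau also lies inside those sections. It is not simply Section 6 against the rest.

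**Stronger readings to avoid.** A reader might infer that a responder at 3.4 ng/kg/min yields only one dose level. That is true of the upward phase only, because weaning adds readings at lower doses if the patient is still ventilated. A reader might also infer that the primary endpoint is compromised. It is not: it belongs to Part I, which has its own titration rule. Nor do the documents show that Part II escalation is unbounded. The visible text gives no maximum dose, but the Pharmacy Manual and the Appendix 2 schematic are not shown.

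**Conclusion.** The inconsistency holds and should be corrected. A patient above 15% at 3.4 ng/kg/min is told both to stop and to go to 6.8, and no visible text resolves this. In size, the upward phase ends at least one 3.4 ng/kg/min step earlier for a responder under Section 6. It runs at least one step further for a patient who plateaus below 15%, with no return stated.

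The consequence is limited to Part II: the maintained dose, the reported dose, and how much of the curve above the 15% dose is observed. The lowest dose giving 15% is unaffected except in patients who plateau below 15%, where the longer escalation in 6.3.4.2 could still reach it. The conclusion rests on the text as written and on the 3.4 ng/kg/min step, with no dose-limiting effect or tolerance limit intervening.

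**What to change.** State one rule in 4.2, 6.2.2, 6.3.3.2, 6.3.4.2 and 10.2.3.1, and keep the synopsis in line. For every patient, whatever the response at 3.4 or 6.8 ng/kg/min, escalate in 3.4 ng/kg/min steps until there is no further improvement, a dose-limiting effect or a tolerance limit. Then return to the previous level with the greatest improvement.

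A bare cross-reference to 10.2.3.1 is not enough. First move its step-back out of the under-15% branch, and cover patients who first reach 15% at 6.8 or have exactly 15% at 3.4. Adding the step-back to the overview in 4.5 is an editorial tidy-up.

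Report the lowest dose with at least a 15% improvement separately from the plateau dose, so that the stated goal and the dose-response purpose each have their own result.

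Cost: clarifying text and one reporting line, with no extra patients. Compared with Section 6, each responder receives at least one more 3.4 ng/kg/min step and its readings, which the plateau rule already plans.
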